### **6.8.3.3 American College of Rheumatology ACR20 Response Definition**

ACR response assessments will be performed only in subjects who meet the CASPAR Criteria (see [Section 6.7](#)). The ACR components evaluations will be used to calculate the subject's ACR response criteria (ACR20 / 50 / 70). ACR20 response indicates a decrease of at least 20% in both the number of tender and swollen joint counts, as well as a 20% improvement in at least three of five scores of individual components:

1. Health Assessment Questionnaire of disability (HAQ-DI).
2. Patient global assessment of disease activity (PtGA) on VAS of 0 to 100.
3. Patient assessment of pain (PtAP) on VAS of 0 to 100.
4. Physician global assessment of disease activity (PGA) on a VAS of 0 to 100.
5. C-reactive protein (CRP) level, mg/dL.

In Part II changes in the ACR20 definition will be taken relative to the Part II baseline for groups that switch treatment in Part II, and relative to the Part I baseline for the other groups.

See appendix 11.3 for detailed instructions on calculating HAQ-DI score.

### **6.8.3.4 Categorical endpoints**

Categorical endpoints include IGA, Scalp IGA, PPPGA, PGIC and PGIS. Number and percentage of subjects with each category of response will be presented by treatment group and visit. Additionally, for PGIS shifts from baseline to each post-baseline visit will be presented.

### **6.8.3.5 Time to PASI75 and IGA responses**

Time to achieve PASI75 and time to achieve IGA response will be summarized separately for the Part I of the study, for the Parts II and III of the study for subjects re-randomized at Week 16 and for the study overall for subjects receiving the same treatment throughout the study.

In the analysis of Part I subjects will be analyzed by treatment groups based on the treatment that the subject received in Part I (see [Section 6.1.1](#)). Time to achieve PASI75 will be defined as the number of weeks from the day of the first dose of the study drug to the first PASI75 assessment in Part I (i.e., up to and including Week 16 visit) when PASI75 is achieved. For subjects who never achieve PASI75 in Part I the time will be censored at the last PASI75 assessment in Part I.

Similarly, time to achieve IGA response in Part I will be defined as the number of weeks from the day of the first dose of the study drug to the first IGA assessment in Part I (i.e., up to and including Week 16 visit) when IGA score of 'clear' or 'almost clear' with at least two-grade reduction from Baseline is achieved. For subjects who never achieve IGA response in Part I the time will be censored at the last IGA assessment in Part I.

The analysis of the Parts II and III will be conducted within subjects who were re-randomized at the start of Part II. In this analysis, subjects will be analyzed by treatment groups based on their treatments in Part II (see [Section 6.1.1](#)). Times will be defined similarly to the analysis of Part I, except they will start at the time of the switch to a new treatment in Part II and will be

censored at the last assessment in the study. Part II baseline will be used when determining PASI and IGA responses.

The analysis for the study overall will be conducted only for subjects who were initially randomized to any dose of SCD-044 and did not switch treatments during the study. In this analysis subjects will be analyzed by treatment groups based on their treatments in Part I. Times will be defined similarly to the analysis of Part I, except then will be censored at the last assessment in the study.

Quartiles of time to achieve PASI75 and time to achieve IGA response (based on the Kaplan-Meier method) with their 95% confidence intervals (using Brookmeyer and Crowley method with log-log transformation) will be calculated by treatment group.

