7.1.11 On-site Visit 18: Visit ([REDACTED])

The following procedures will be performed at Visit 18:

Confidential

1. A urine pregnancy test will be conducted for all females of childbearing potential (see Section 5.4)

The following procedures will be performed by an independent safety team:

2. The occurrence of all AEs & AESIs will be assessed and documented following the procedures in Sections 5.9, 10.1, and 10.3.
3. A query for PML (progressive multifocal leukoencephalopathy) will be performed (See Section 5.10)
4. A query for PRES (Posterior reversible encephalopathy syndrome) will be performed (See Section 5.11)
5. The Subject's diary provided at the previous visit will be collected and reviewed.
6. The returned study drugs will be counted
7. The use of concomitant medications since the previous study visit will be documented and assessed. (See Section 5.8)
8. Vital signs (blood pressure, pulse, respiratory rate and oral body temperature) will be documented. Subjects must remain in a seated or supine position for at least 5 minutes before vital signs are obtained. (See Section 5.3)
9. A blood sample will be collected for Hematology (See Section 5.5)
10. Independent Safety Assessor review:
 - Safety Lab Alerts
 - [REDACTED]
 - As available
 - i. Lab results
 - ii. Exam results

The following procedures will be performed prior a subject discharged from a clinic:

11. The following will be dispensed during Visit 18:
 - 2 UPT to be performed at home at weeks 44 and 48 – *for female Subjects of childbearing potential* (see section 5.4)
 - The study drug assembled for Visit 18
 - A diary card with instructions and to record the study drug use, health changes and concomitant medication
12. A general safety review before discharge
13. Visit 19 (Study Day 365 ± 3 Days; before 12 noon) will be scheduled and the Subject will be instructed to bring the Study Product (used, unused, and partially used packs) and Subject diary with him or her to this visit.
14. Phone calls will be scheduled at the study weeks 44 and 48 to collect information on the study drug use, UPT, health changes and concomitant medication.

7.1.12 On-site Visit 19: End of Treatment Visit (Week 52 / Day 365 ± 3 Days; before 12 noon)

The visit 19 must be scheduled in a morning to allow the dosing before 12 noon.

The following procedures will be performed at Visit 19:

1. A urine pregnancy test will be conducted for all females of childbearing potential (see Section 5.4)

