- Part II Baseline is defined as the last assessment, scheduled or not, prior to the first dose of the study drug in Part II. Part II baseline will be used in analysis of findings collected in Parts II, III and IV for subjects who were re-randomized in Part II to another treatment (i.e. SCD-044 [ ] or [ ] after being treated with Placebo in Part I or to SCD-044 [ ] after being treated with SCD-044 [ ] or [ ] in Part I). Throughout this SAP, if the word “baseline” is used without qualification “Part I” or “Part II”, it will refer to Part I baseline.

In by-visit summaries, only data collected on scheduled visits/timepoints will be summarized. Data from unscheduled assessments will be included in listings and may be used in determination of baseline if applicable.

Relative days will be calculated relative to date of first dose of the study drug. Relative days will be calculated as follows only when the full assessment date is known (i.e., partial dates will have missing relative days).

For assessment on or after the day of first dose of the study drug:

Relative Day = Date of Assessment – Date of First Dose of Study Drug+1.

For assessment before the day of first dose of the study drug:

Relative Day = Date of Assessment – Date of First Dose of Study Drug.

All dates will be displayed in DDMMYY format.

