## 6.8 Efficacy Analyses

### 6.8.1 Imputation of the primary and key secondary endpoints

All subjects in the ITT population with the following intercurrent events prior to Week 16 will be imputed as non-responders for both the primary endpoint and key secondary endpoint.

- taking prohibited medications prior to Week 16
- discontinuing from the study due to lack of efficacy, protocol deviation or AE prior to Week 16

Subjects who did not have intercurrent events prior to Week 16, and either do not have a Week 16 PASI assessment or do not have a PASI baseline will be referred to as “subjects missing at random” for the primary endpoint. Similarly, subjects who did not have intercurrent events prior to Week 16, and either do not have a Week 16 IGA assessment or do not have an IGA baseline will be referred to as “subjects missing at random” for the key secondary endpoint.

The PASI values of these subjects will be imputed using multiple imputations (MI) approach under the “missing at random” (MAR) assumption. For each subject who is “missing at random” in the ITT population 50 imputations will be performed using Fully Conditional Specifications (FCS) regression imputation model with the factors for gender, prior biologic therapy (Yes/No), PASI score at baseline and weeks 4, 8, 12 and 16. All subjects in the ITT population will be used in the model. Imputed PASI scores will be rounded to 1 decimal place and restricted to the range 0 to 72. For all imputed record PASI75 response will be calculated based on the imputed PASI value using the regular PASI75 definition, i.e. 75% reduction from baseline in the PASI score. See section 11.4.1 for sample SAS code.

The key secondary endpoint values (i.e. the binary outcomes of whether the subject achieved the IGA response or not) will also be imputed using multiple imputations (MI) approach under the “missing at random” (MAR) assumption. For each subject who is “missing at random” in

the ITT population 50 imputations will be performed using Fully Conditional Specifications (FCS) logistic regression imputation model with the factors for gender, prior biologic therapy (Yes/No), IGA grades at baseline and weeks 4, 8, and 12. All subjects in the ITT population will be used in the model. See section 11.4.2 for sample SAS code.

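### SAP 6.8.3.5 sets no scheduled-week rule for time to PASI75/IGA response; on the natural reading, Kaplan-Meier can report quartiles that were never reached.

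*SAP*

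**What the plan says.** For Part I, SAP 6.8.3.5 runs the clock as follows: "Time to achieve PASI75 will be defined as the number of weeks from the day of the first dose of the study drug", ending at the first Part I assessment at which the response is met. Never-responders are handled by "For subjects who never achieve PASI75 in Part I the time will be censored at the last PASI75 assessment in Part I". IGA has the matching rule: "For subjects who never achieve IGA response in Part I the time will be censored at the last IGA assessment in Part I". The Parts II/III analysis uses similar definitions but starts at the switch and uses the Part II baseline. The overall analysis covers subjects who stay on one active dose and censors at the last assessment in the study.

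The only summary stated is "Quartiles of time to achieve PASI75 and time to achieve IGA response (based on the Kaplan-Meier method) with their 95% confidence intervals", by treatment group. The section gives no scheduled-week time, rounding rule, common censoring time or interval-censored method. Elsewhere the SAP counts elapsed time from actual dates: "Relative Day = Date of Assessment – Date of First Dose of Study Drug+1" (SAP 6.1).

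**The concern.** Response can be observed only at planned visits, each with a window of days. At the last visit of an analysis period, every subject still at risk either responds or is censored, on his or her own day. Suppose the window is ±3 days around Day 113. A non-responder seen on Day 110 is then dropped before a responder seen on Day 116 is counted, so the later responder is divided by a smaller risk set. The days between them are scheduling scatter, but Kaplan-Meier treats them as follow-up. The effect needs neither dropout nor any link between visit timing and response. Earlier windows are unaffected, because non-responders there stay at risk.

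Time to PASI75 and time to IGA response are both listed secondary endpoints. A dose could be given a median time to PASI75 although fewer than half of its subjects responded, in conflict with the responder percentages in the same report.

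**Working it through.** The documents state no figure for this analysis, so there is nothing to reproduce.

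**Inputs**
- Part I assessments: "PASI score at baseline and weeks 4, 8, 12 and 16" (SAP 6.8.1). Week 16 is taken as Day 16 × 7 + 1 = 113, matching Week 52 as Day 365.
- Arm size: about 240 subjects at 1:1:1:1 (Protocol 4.1), so 240/4 = 60.
- Week 16 window: redacted. Two windows visible elsewhere are assumed: ±1 day (Visit 14, given in Protocol 7.1.6) and ±3 days ("Visit 19 (Study Day 365 ± 3 Days; before 12 noon) will be scheduled", Protocol 7.1.11).
- Cumulative response at Weeks 4/8/12/16, assumed: 5/15/25/35%, 2/7/13/20% and 1/3/5/8%.
- Visit days uniform within the window and independent of response; no dropout; weeks = days/7.

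**Closed form.** Let p be the share of those at risk who respond at the last visit, and K the number of days in the window (3 for ±1, 7 for ±3). Counting back from the last day of the window, the daily hazards are p, p/2, …, p/K. The estimated response within the window is therefore 1 − ∏(1 − p/k) for k = 1 to K, where the correct value is p.

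For a true 35%: p = (0.35 − 0.25)/(1 − 0.25) = 0.1333.
- ±1 day: 0.8667 × 0.9333 × 0.9556 = 0.7729. End of curve = 1 − 0.75 × 0.7729 = 42.0%.
- ±3 days: 0.7729 × 0.9667 × 0.9733 × 0.9778 × 0.9810 = 0.6975. End of curve = 1 − 0.75 × 0.6975 = 47.7%.

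The same formula with p = 7/87 and p = 3/95 gives the other two rows.

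| True response | End of curve, ±1 | End of curve, ±3 | Scheduled weeks |
|---|---|---|---|
| 35% | 42.0% | 47.7% | 35% |
| 20% | 25.3% | 29.7% | 20% |
| 8% | 10.4% | 12.5% | 8% |

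**Simulation of the reported statistic** (repeated runs of 2,000 or more arms of 60 each; mean end-of-curve values agree with the table). A quartile is counted as false only if the estimate reaches it while the arm's own observed response is below it. Rates are shares of all arms.

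| True response | False quartile | ±1 | ±3 | Scheduled weeks |
|---|---|---|---|---|
| 35% | median | about 15% | 36–38% | 0% |
| 20% | first quartile | 27–29% | 44–45% | 0% |
| 8% | first quartile | about 1% | about 7% | 0% |

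**Where it applies after Week 16** (by reasoning; not simulated)
- Week 28: affected. Under Protocol 7.1.9, subjects below PASI75 stop there, so their censoring falls in the same window as the Week 28 responses.
- Week 52, PASI75, overall analysis: not affected. Only subjects at or above PASI75 continue past Week 28, and non-switchers are measured from the Part I baseline, so everyone still treated has already had the event.
- Week 52, IGA, or switchers measured from the Part II baseline: possible. A subject may pass the Week 28 threshold without having met the analysed response.

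**The case against.** The strongest reply is that SAP 6.8.3.5 says only that time is in weeks. It never says actual days or fractional weeks, and the actual-date formula in SAP 6.1 is for relative day and is not cited in 6.8.3.5. If weeks were rounded to the nearest whole number, the artefact could vanish: elapsed days 109 to 115 give 15.57 to 16.43, all rounding to 16. That stands as a limit on the claim, but the text states no rounding. Rounding alone is also fragile: on the SAP's relative-day count, Day 116 is 116/7 = 16.57, which rounds to 17.

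It can also be said that only quartiles are planned, so an inflated end of the curve is not itself a stated output. A false quartile falls at about 16 weeks, usually with an upper confidence limit that cannot be estimated. Responder percentages with confidence intervals are reported alongside (SAP 6.8.3.2). This is fair and keeps the consequence small. A reader comparing the tables could see the conflict, but the reported quartile would still be wrong.

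A placebo-like arm is barely affected on the reported statistic; this also stands.

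**Conclusion.** The point holds, with limited consequences. As written, the natural derivation biases the final Kaplan-Meier step upward and can produce quartiles that were not reached. This is most likely when true response lies somewhat below 25% or 50%. The sizes above rest on days/7 with no rounding, an assumed ±1 or ±3 day window at Week 16, 60 per arm, uniform visit timing and no dropout.

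Three stronger readings are tempting and are not supported:
- That the SAP prescribes actual-day timing, so that false quartiles will occur. The basis is inferred from silence and the Week 16 window is redacted; "can occur" is the limit.
- That every analysis is affected through Week 52. PASI75 in the overall analysis is not, because subjects below PASI75 stop at Week 28.
- That the trial's main conclusions are touched. The Week 16 primary and key secondary analyses do not use these times. The affected summaries are descriptive, and SAP 6.1.2 draws no inference from other endpoints.

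It should be corrected because these quartiles are the only stated summary of two secondary endpoints.

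**What to change.** Add to SAP 6.8.3.5, for both PASI75 and IGA, that event and censoring times are the scheduled visit week of the assessment, with events placed before censorings at ties:
- Part I: Weeks 4, 8, 12 and 16.
- Parts II/III: scheduled weeks after the Week 16 switch. Weeks 20, 28 and 52 become 20 − 16 = 4, 28 − 16 = 12 and 52 − 16 = 36.
- Overall: the scheduled study weeks.

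With no dropout, the Part I estimate at Week 16 then equals the observed proportion of responders. An interval-censored (Turnbull) estimate would also work but is not needed. The cost is one sentence and a change to the derivation, with no new data.

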### 2.2 Primary Estimand

The primary estimand is defined as follows:

Population of interest	Subjects with moderate to severe plaque psoriasis
Outcome Measure/Endpoint	Achieving at least 75% improvement in PASI at Week 16
Treatment	SCD-044 [REDACTED] and placebo once daily
Intercurrent Event	

Use of prohibited medications (as determined during blinded data review)

Early treatment discontinuation due to lack of efficacy, protocol deviation or AEs

 
Composite strategy will be applied to these intercurrent events and the subjects with intercurrent events will be treated as non-responders.

Population-level Summary Measure	Difference in proportions between each the active treatment arms and placebo arm

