### 6.1.2 Adjustment for multiplicity

No adjustment for multiplicity will be needed for the analysis of the primary and key secondary endpoints due to the step-down testing approach described below in this section. P-values for other endpoints, if calculated, will be presented nominally, without multiplicity adjustment. No inferences will be drawn from these p-values.

[REDACTED]

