### **6.1.3 Handling of Withdrawals and Missed Data**

In the primary analysis of the primary and the key secondary endpoint subjects with intercurrent events will be treated as non-responders and other missing values will be imputed using multiple imputation approach. See section 6.8.1 for more details. Last Observation Carried Forward (LOCF) and Active Treatment Worst Case (ATWC) imputations as well as tipping-point analysis will be explored in the sensitivity analyses (see section 6.8.2.2). All other endpoints will be summarized as collected without imputations and without any special handling for the intercurrent events.

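### Time to PASI75 and IGA response censors subjects who stop for lack of efficacy or an AE at their last assessment, so the Kaplan-Meier summary is equal to or more favourable than one that keeps them as never-responders

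*SAP*

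**What the plan says.** SAP 6.8.3.5 measures time from first dose to the first assessment at which the response is seen. For PASI75 in Part I: "For subjects who never achieve PASI75 in Part I the time will be censored at the last PASI75 assessment in Part I". For IGA: "For subjects who never achieve IGA response in Part I the time will be censored at the last IGA assessment in Part I". Neither sentence asks why an assessment was the last one. The output is "Quartiles of time to achieve PASI75 and time to achieve IGA response (based on the Kaplan-Meier method) with their 95% confidence intervals", by treatment group. The visible text names no test, hazard ratio or Week 16 cumulative rate. The Parts II/III and whole-study analyses are defined by analogy, with censoring at the last assessment in the study.

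For the Week 16 analyses, SAP 2.2 lists two intercurrent events: use of prohibited medication, and "Early treatment discontinuation due to lack of efficacy, protocol deviation or AEs". It then says: "Composite strategy will be applied to these intercurrent events and the subjects with intercurrent events will be treated as non-responders". SAP 2.4 repeats this for IGA. SAP 6.8.1 carries it out: subjects with these events before Week 16 "will be imputed as non-responders for both the primary endpoint and key secondary endpoint".

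SAP 6.1.3 sets the rule for everything else: "All other endpoints will be summarized as collected without imputations and without any special handling for the intercurrent events". Both times to response are other secondary endpoints (protocol 9.8), so that sentence governs them. SAP 6.1.2 adds: "P-values for other endpoints, if calculated, will be presented nominally, without multiplicity adjustment", and says that no inferences will be drawn from such p-values.

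**The concern.** Kaplan-Meier assumes non-informative censoring: a censored subject has the same future chance of response as the subjects still under observation. A subject who leaves because the drug is not working contradicts that assumption by the reason for leaving. The protocol's Study Overview even allows a subject who worsens to be withdrawn as a treatment failure. Under 6.8.3.5 that subject is censored, not counted as never having responded. In the other direction, a subject who first reaches PASI75 after starting a prohibited psoriasis treatment counts as an event.

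For the same two outcomes over the same 16 weeks, the SAP has already decided in 2.2 and 2.4 that these events mean non-response. The time-to-response summary uses the opposite meaning and does not tell the reader that its quartiles rest on non-informative censoring. At stake is how two listed secondary endpoints read. No confirmatory test is affected.

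**Working it through.** **Inputs.** From the documents: about 240 subjects at 1:1:1:1 (protocol 4.1), so 240/4 = 60 per arm; Part I post-baseline PASI assessments at Weeks 4, 8, 12 and 16 (SAP 6.8.1). The documents state no figure for this endpoint and show no response or dropout rates, so there is no plan figure to reproduce. All rates below are assumptions, and visits are placed on the nominal grid.

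**Direction.** At each visit j, let e be first responses and r the number at risk. The SAP rule gives 1 − ∏(1 − e_j/r_j), with intercurrent-event dropouts removed from r. Keeping them as never-responders leaves e unchanged and makes r larger, so each factor (1 − e_j/r_j) is larger and the cumulative response smaller. With no other missing data it is then simply responders/60. The SAP figure is never below it, and is above it whenever such a dropout precedes a later response in the same arm. Not counting responses after prohibited medication can only lower the figure further.

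**Counts, 60 per arm.** Assume 2, 4, 5 and 3 first responses at Weeks 4, 8, 12 and 16 (14 in all), with dropouts split equally after Weeks 4, 8 and 12. Never-responder figure: 14/60 = 23.3% in every row.

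| Dropouts | SAP rule at Week 16 | Result | Excess (points) |
|---|---|---|---|
| 0 | 1 − (58/60)(54/58)(49/54)(46/49) | 23.3% | 0 |
| 6 (10%) | 1 − (58/60)(52/56)(45/50)(40/43) | 24.9% | 1.5 |
| 9 (15%) | 1 − (58/60)(51/55)(43/48)(37/40) | 25.7% | 2.4 |
| 15 (25%) | 1 − (58/60)(49/53)(39/44)(31/34) | 27.8% | 4.4 |

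**Range of response levels.** Let h be the chance of a first response at each visit among those at risk, and d the dropout probability among non-responders in each interval after Week 4 (2% to 12%). The SAP figure is 1 − ∏(1 − h_j). The never-responder figure is the sum of h_j times the proportion still at risk.

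| Scenario (h at Weeks 4, 8, 12, 16) | SAP rule | Never-responder figure | Total dropout | Excess (points) |
|---|---|---|---|---|
| Low (.02, .05, .06, .08) | 19.5% | 18.8% to 15.4% | 5.5% to 29.7% | 0.7 to 4.1 |
| Mid (.05, .10, .12, .15) | 36.0% | 34.8% to 29.0% | 5.0% to 27.4% | 1.3 to 7.0 |
| High (.08, .18, .22, .25) | 55.9% | 54.0% to 45.5% | 4.4% to 24.5% | 1.9 to 10.4 |

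The last cell in full, for d = 12%: SAP rule 1 − (.92)(.82)(.78)(.75) = 55.9%; never-responder figure .0800 + .1457 + .1285 + .1003 = 45.5%.

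**Effect on the planned output.** Quartiles often stay put on a 4-week grid. In the mid scenario the 25th percentile is Week 16 under both rules throughout. They move when the curve is near a quartile. With 14 responders and 9 or 15 dropouts, the 25th percentile is Week 16 under the SAP rule (25.7% or 27.8%) and not reached otherwise (23.3%). In the high scenario with about 17% or more dropout, the median is Week 16 under the SAP rule and not reached otherwise (48.7% at 16.9% dropout).

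**Later parts.** Protocol 7.1.9 ends dosing at Week 28 for a PASI response below 75. The Parts II/III and whole-study analyses therefore censor some subjects because of their outcome, by design.

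**The case against.** The strongest reply is that the SAP announces the difference. A reader might infer that 6.8.3.5 breaks the SAP's composite rule. It does not: 2.2, 2.4 and 6.8.1 confine that rule to the two Week 16 endpoints, and 6.1.3 exempts all others. What remains is an unexplained difference of estimand. That objection stands as far as it goes. But stating a choice does not make the censoring non-informative, and nothing in 6.8.3.5 tells the reader that the quartiles depend on it.

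Three other tempting readings also fail.

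- **The curve at Week 16 should equal the Week 16 response rate.** It need not under any censoring rule. One counts first response at any visit, the other status at Week 16, so a subject who responds at Week 8 and then relapses differs between them. The primary analysis also multiply imputes other missing data. A mismatch is not evidence of a censoring fault.
- **The excess is largest in the arm with most dropout.** Not in general. It also depends on later response: 29.7% dropout with low response gives 4.1 points, 24.5% with high response gives 10.4.
- **The rule favours active treatment.** Lack-of-efficacy and AE dropout may fall in different arms, so the contrast with placebo has no fixed direction.

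It is also fair to say that the output is descriptive, any p-values are nominal, and no trial decision rests on it. That limits the importance of the point but does not answer it.

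**Conclusion.** The point holds as a modest, inexpensive improvement. Within each arm, Kaplan-Meier cumulative response under 6.8.3.5 is equal to or higher than the figure with intercurrent-event subjects kept as never-responders. The direction follows from the algebra. The size does not come from the documents: under the assumed scenarios it is zero with no such dropout, about 1 to 5 points at roughly 5–15%, and up to about 10 points at about 25% with high response. These figures count only dropout from the listed intercurrent events. Other withdrawals are not treated as non-response in SAP 6.8.1 and would not add to the gap. The reported quartiles may show no change, or may change from Week 16 to not reached. The documents support neither a breach of the composite rule nor a claim of bias towards active treatment.

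**What to change.** Amend SAP 6.8.3.5, and add the matching exception to 6.1.3. In Part I, censor a subject with an intercurrent event and no earlier response at the nominal Week 16 time, so that the subject stays in the risk set as a never-responder. Do not count a first response after prohibited medication as an event. Keep last-assessment censoring for other missing data. Because 6.8.3.5 counts weeks from first dose, either analyse in nominal visit weeks or place this censoring no earlier than the last Week 16 assessment. Otherwise these subjects leave the risk set just before responses recorded a little late.

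Apply the same principle to the Parts II/III and whole-study analyses, using the end of the relevant period, and state how subjects whose dosing ends at Week 28 on PASI response are handled. If the sponsor prefers the present rule, the minimum is a sentence saying that the quartiles assume non-informative censoring.

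No new data are needed. Reasons for discontinuation are already recorded (protocol 4.7, SAP 6.2), and prohibited medication is already settled at blinded data review (SAP 2.2). The cost is a short SAP edit and slightly less favourable response times.
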